5.4.8 Vital Signs

Actual values and changes from baseline in vital signs (heart rate, systolic blood pressure, diastolic blood pressure, weight, height [baseline only], and BMI) will be summarized using descriptive statistics by treatment group and post-baseline time point. Baseline is defined as the last value prior to the first dose of study medication.

Vital signs data will be listed for each patient, with increases from baseline of >15 mmHg in systolic or diastolic blood pressure flagged.

5.4.9 Electrocardiogram (ECG)

Shift tables for ECG data from baseline to end-of-study will be provided by treatment group. The data will be categorized as 'Normal'; 'Abnormal, not clinically significant'; and 'Abnormal, clinically significant.' Listings of ECG data will include only those records where the baseline ECG was either 'Normal' or 'Abnormal, not clinically significant', but the end-of-study ECG was marked as 'Abnormal, clinically significant'.

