#### Primary Safety Endpoint

The primary endpoint for this study is general safety, which includes AEs, clinical safety laboratories, PEs, vital signs, and ECGs.

The summarization of AEs will include only treatment-emergent AEs (TEAEs), defined as AEs that begin or worsen after randomization and ingestion of the first dose of study drug. TEAEs and SAEs will be summarized by system organ class (SOC), severity, and relationship to study drug for each treatment group. Deaths, withdrawal from study treatment due to AEs, and withdrawal from the study due to AEs will each be summarized by treatment group.

Clinical safety laboratories, including hematology, blood chemistry, coagulation, HbA1C, glucose, and urinalysis; PE findings; vital signs; ECG readings; and weight will be summarized by the value and by change from baseline in the value (where appropriate) at each post-baseline time point.

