### **11.1.5.    *Electrocardiogram***

ECG collection will be preceded by a 10-minute rest time during which the patient will remain in the supine position. At all time points, ECGs will be collected prior to blood collection. ECGs will be assessed using machine readings and physician review.

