3.2 Primary Safety Endpoints

The primary safety endpoint for this study is general safety, which includes adverse events (AEs), clinical safety laboratories, physical examinations (PEs), vital signs, and electrocardiogram (ECGs).

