3.2.3 ECG, Vital Signs and PE

The evaluation of ECG and vital signs (including heart rate, systolic blood pressure, diastolic blood pressure, weight, height [baseline only], and body mass index [BMI]), will be based on the observed values. For ECGs, shifts from baseline to end-of-study will be summarized. For vital signs, observed values and changes from baseline will be summarized for all post-baseline study visits. Listings of PE data will include only those records where the body system at the baseline PE was normal, but the body system at a post-baseline PE was marked as 'Change from previous exam, clinically significant.'

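### The SAP summarises ECGs only as a three-category shift table and a listing, without declaring the departure from the protocol's value-and-change plan, so a mean interval shift would not be shown

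*SAP*

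**What the plan says.** Both documents make ECGs part of the primary safety endpoint. In the protocol synopsis: "The primary endpoint for this study is general safety, which includes AEs, clinical safety laboratories, PEs, vital signs, and ECGs". SAP 3.2 gives the same five components.

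The two documents differ on the summary. The synopsis says: "ECG readings; and weight will be summarized by the value and by change from baseline in the value (where appropriate) at each post-baseline time point". Protocol 11.1.5 adds: "ECGs will be assessed using machine readings and physician review". SAP 3.2.3 opens by basing the ECG and vital-sign evaluation on observed values, but then separates the two: vital signs get observed values and changes from baseline, while "For ECGs, shifts from baseline to end-of-study will be summarized". SAP 5.4.9 confirms this: "Shift tables for ECG data from baseline to end-of-study will be provided by treatment group", and "The data will be categorized as 'Normal'; 'Abnormal, not clinically significant'; and 'Abnormal, clinically significant". The only other ECG output there is a listing of patients who move into the clinically significant category at end of study.

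SAP section 2 says that the SAP prevails over the protocol on analysis. SAP 4.6, on changes from the protocol's planned analyses, has three items and none concerns ECGs. The summary of changes at the end of the SAP does not mention them either.

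**The concern.** The three-level category is an overall judgement on a whole tracing, made in a study with about 125 sites. It responds to gross abnormality in an individual. A drug effect on conduction or repolarisation could instead appear as a few milliseconds of average prolongation across the treated arm, with few patients changing category. A patient already rated abnormal but not clinically significant at baseline can have a longer interval at Week 52 and stay in the same cell.

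The study exists to characterise long-term safety against placebo. If the only ECG output is the category shift, the report could show no ECG difference between arms while the readings contain one. Because the SAP governs and does not declare the departure, someone who knows only the synopsis would expect a numeric summary that is not planned.

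**Working it through.** The documents state no ECG figure to reproduce, so the check is a comparison of texts followed by an illustration of size.

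**Comparison**

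| Item | Protocol synopsis | SAP |
|---|---|---|
| ECG summary | Value and change from baseline, where appropriate | Three-category shift table and listing (3.2.3, 5.4.9) |
| Time points | Each post-baseline time point | Baseline to end of study |
| ECG intervals | Not named | Not summarised |
| Heart rate | Vital signs by value and change, where appropriate | Value and change, as a vital sign (5.4.8) |
| Departure declared | n/a | Not in 4.6, not in the summary of changes |

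The schedule of events (Protocol Appendix 1) places a single 12-lead ECG at Day 1 and at Week 52/end of study. There is therefore one scheduled post-baseline comparison.

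**Inputs for the illustration**
- From SAP 4.4: 1170 and 585 patients expected at 12 months or more.
- Assumed, because the documents give none: SD of the interval change 15, 20 or 25 ms; for the categorical version, QTc mean 420 ms, SD 22 ms, and a single cut-off at 450, 460 or 480 ms.
- Two-sided 0.05, normal approximation.

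**Numeric summary.** SE = SD × √(1/1170 + 1/585); half-width of the 95% CI = 1.96 × SE.

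| SD (ms) | SE (ms) | Half-width (ms) | Power for 5 ms |
|---|---|---|---|
| 15 | 0.76 | 1.5 | >99.9% |
| 20 | 1.01 | 2.0 | 99.9% |
| 25 | 1.27 | 2.5 | 98% |

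**Single cut-off.** With c the cut-off, p0 = 1 − Φ((c − 420)/22) and p1 = 1 − Φ((c − 420 − shift)/22). Power = Φ(|p1 − p0|/SE − 1.96), where SE = √(p1(1 − p1)/1170 + p0(1 − p0)/585). For a 5 ms shift:

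| Cut-off (ms) | p0 | p1 | SE | (p1 − p0)/SE | Power |
|---|---|---|---|---|---|
| 450 | 8.63% | 12.79% | 1.52% | 2.74 | 78% |
| 460 | 3.45% | 5.58% | 1.01% | 2.11 | 56% |
| 480 | 0.32% | 0.62% | 0.33% | 0.92 | 15% |

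At 480 ms the expected counts are about 2 placebo patients (585 × 0.32%) and 7 on ETC-1002 (1170 × 0.62%). For a 10 ms shift, power is above 99% at 450 and 460 ms and 57% at 480 ms.

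In every row, categorising loses power against the numeric summary. How much it loses depends on the assumed cut-off.

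**The case against.** The strongest reply is that the protocol's commitment is conditional. The same sentence covers physical findings and urinalysis, which are largely categorical, so it cannot promise a numeric summary for every item; a shift table is a reasonable categorical version of value and change. It is visible only in the synopsis, and Protocol 12.5 is partly redacted. No visible passage names PR, QRS or QT/QTc as something to summarise, or plans a between-arm difference, a confidence interval or QTc cut-offs. This stands as a limit on what can be called a departure. It does not remove the point: machine-read intervals are numeric, so value and change would be appropriate for them, and SAP 3.2.3 itself refers to observed values.

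The design also limits what a numeric summary can show. There is one scheduled post-baseline single ECG, and Protocol 9.2 delays dosing on clinic days until procedures are finished. The AESI list in SAP Appendix 2 has no QT or conduction term, and the redacted background may deal with interval effects elsewhere. Clinically significant ECG changes are reported as adverse events (Protocol 11.1.5.1). That captures individual events but would not reveal a small mean shift.

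Three stronger readings are tempting, and the documents do not support them:
- A reader might infer that a rate shift would also be missed. It would not: SAP 5.4.8 summarises heart rate by value and change, and vital signs are taken at Weeks 4, 8, 12, 24, 36 and 52.
- A reader might take 15% as the power of the planned analysis. That figure belongs to one assumed boundary, and the shift table also has a boundary between normal and abnormal.
- A reader might assume that many patients have an abnormal ECG at baseline. This is plausible in a population with HeFH or ASCVD, but the documents give no rate.

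**Conclusion.** The point holds in a limited form. The governing SAP gives ECGs a three-category shift table and a listing, where the protocol synopsis conditionally plans value and change, and it does not list the difference. A mean interval shift would therefore not appear in the ECG output for this component of the primary safety endpoint.

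Under the assumed SDs, a numeric summary would be precise enough to be informative, with a half-width of 1.5 to 2.5 ms. The advantage over categories for a 5 ms shift runs from moderate (78% power against 98% or more) to large (15% against 98% or more). Both calculations simplify, since a real ECG call is a composite judgement, and the sample sizes assume that every patient expected at 12 months has both tracings.

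The documents do not show that interval values reach the database, so whether the numeric summary is feasible cannot be confirmed from them. No confirmatory test is affected. This is an inexpensive improvement to a safety summary and a reconciliation of the two documents.

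**What to change.** Amend SAP 3.2.3 and 5.4.9 to summarise the available machine-read intervals (for example PR, QRS and QT/QTc) at Day 1 and Week 52/end of study, by arm, as value and change from baseline. Add the between-arm mean difference in change with its 95% CI, stated as an addition to the protocol's descriptive plan. Keep the three-category shift table and the listing as supportive.

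If numeric intervals were not captured, say so in SAP 4.6 and give the reason for departing from the synopsis.

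The cost is SAP wording and one or two tables. The possible extra burden is data transfer, if some sites hold the machine values only on the ECG report. The gain is bounded by having a single post-baseline tracing per patient.

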5.5 Pharmacokinetic Endpoints and Other Biomarkers

Plasma concentrations of ETC-1002 and its metabolite ESP15228 will be determined from 6 mL whole blood samples collected from patients at Weeks 12, 24, and 52 for those patients randomized prior to Amendment 3 in the EU and Amendment 4 in the US. At the time of sample collection, the date and time of blood draw and the last 2 doses of study medication will be collected. Any PK concentration with sample draw time outside of the 18-30 hours from last dose of IMP will be excluded from the summary.

In all data presentations (except listings), concentrations below the limit of quantitation (BLQ) will be set to zero. In listings, BLQ values will be reported as less than the lower limit of quantification (<LLQ).

6 DMC Analyses

Refer to DMC charter.

7 Reference

2. World Health Organization (WHO) Fact Sheet No 317 Updated January 2015.
3. Robinson JG. Management of Familial Hypercholesterolemia: A Review of the recommendations from the National Lipid Association Expert Panel on Familial Hypercholesterolemia. *J Managed Care Pharm*. 2013;19(2):139-49.
4. Pharmacokinetics in Patients with Impaired Renal Function — Study Design, Data Analysis, and Impact on Dosing and Labeling. FDA Draft Guidance. March 2010
7. Brendan M.Everett, TobiasKurth, Julie E.Buring, Paul M.Ridker. “The Relative Strength of C-Reactive Protein and Lipid Levels as Determinants of Ischemic Stroke Compared With Coronary Heart Disease in Women.” *Journal of the American College of Cardiology* (2006), Volume 48, Issue 11, Pages 2235-2242.

8 Appendices

Appendix 1: Schedule of Events (Patient Visit Schedule)

Visit	Screen	Treatment										
	S1 ^{1,2}	T1	T2	T3	T4	T4.1	T4.2 phone	T5	T5.1	T5.2 phone	T6	T7 EOS ³
Week	Wk -2	Wk 0	Wk 4	Wk 8	Wk 12	Wk 16	Wk 20	Wk 24	Wk 28	Wk 32	Wk 36	Wk 52
Procedure	Day -16 to -4	Day 1	Day 29±3	Day 57±3	Day 85±3	Day 112±3	Day 140±3	Day 169±7	Day 196±7	Day 224±7	Day 253±7	Day 365±7
Informed Consent	X											
Enrollment Criteria	X											
Demographics	X											
Medical History	X											
HeFH Status Determination	X											
Concomitant Medications	X	X	X	X	X	X	X	X	X	X	X	X
Adverse Event Recording		X	X	X	X	X	X	X	X	X	X	X
Physical Exam		X										X
Weight ⁴	X	X	X	X	X			X			X	X
Height/BMI	X											
12-Lead ECG ⁵		X										X
Vital Signs ⁶	X	X	X	X	X			X			X	X
Serology ⁷	X											
Serum Pregnancy and/or FSH ⁸	X											
Urine Pregnancy Test ⁸		X										
TSH	X											
Clinical Safety Labs ⁹	X	X	X	X	X			X			X	X
Additional Clinical Safety Labs ¹⁰						X			X			
Basic Fasting Lipids ¹¹	X	X	X	X	X			X			X	X
HbA _{1C}	X	X			X							X
10 mL reserve sample		X			X			X				X
Genetic sample	X											
apoB		X			X			X				X
hsCRP		X			X			X				X
Diet and exercise counseling ¹²	X	X	X	X	X	X		X	X		X	
Plasma PK ¹³					X			X				X
Establish Patient Eligibility		X										
Randomization		X										
IWRS Contact	X	X			X			X			X	X ¹⁴
Double-blind Drug Dispensing ¹⁵		X			X			X			X	
Drug Return/Compliance			X	X	X			X			X	X
Schedule next visit	X	X	X	X	X			X			X	X ¹⁶

NOTE: For patients who withdraw from IMP treatment, but consent to be followed for safety assessments and return to clinic for these visits, the visits will occur according to the protocol schedule. Safety assessments should include clinical safety and basic lipid laboratories (except for apoB and hsCRP), adverse events, PE, vital signs, and ECGs. For patients who withdraw from IMP treatment, but consent to be followed for safety assessments by phone, the telephone contacts will occur according the protocol schedule with information regarding current health status and to collect information on AEs (eg, recent procedures, hospitalizations, and if the patient has died, the cause of death). If a patient does not provide consent to be followed for safety assessments per the protocol (either by returning to clinic or by phone), Visit T7 will be considered the EOS/Early Withdrawal from study and no further visits will be scheduled.

- ¹ An optional visit approximately 1 week later MAY be completed if patient fails to meet a lipid entry criterion. If this optional visit is completed, the mean of lipid values from both visits will be used to determine eligibility.
- ² An optional visit between Visits S1 and T1 may be completed if the patient's DBP and/or SBP meet the exclusion criteria levels. Patients may randomize after blood pressure medications have been adjusted, the patients have been on stable doses of blood pressure medications for at least 2 weeks, and the repeat blood pressure values (DBP and/or SBP) do not meet exclusionary values. An optional visit between Visit S1 and T1 may be completed to determine eligibility if the patient's eGFR, ALT, AST, and/or TB meet exclusion criteria levels. If this optional visit is completed, the repeated value will be used to determine eligibility.
- ³ All procedures will be completed for all patients at either End of Study (EOS) if completing the study or early withdrawal.
- ⁴ Body weight will be measured in the morning while fasting, using consistent scales, after voiding, and without shoes and outerwear (eg, coats).
- ⁵ Single 12-lead ECG will be collected prior to any blood sample collection.
- ⁶ Vital signs will include DBP, SBP, and HR and will be collected prior to any blood sample collection. Patient will rest for 5 minutes prior to assessments
- ⁷ Serology for HBsAg, HCV
- ⁸ Serum pregnancy test completed in premenopausal women only. *Urine pregnancy test is completed in premenopausal women who are able to become pregnant. FSH test is completed in women <55 years old and >1 year without menses*
- ⁹ Clinical safety labs include hematology, blood chemistry, and urinalysis at all visits. *These will also be conducted 4 weeks after any changes in the patient's lipid-modifying treatment. Coagulation is included at Screening (Visit S1) for all patients, and then only in patients receiving anticoagulant therapy that in the investigator's judgement requires monitoring at Baseline (Visit T1) and 3 to 5 days post Visit T1. Please refer to ICON laboratory manual for detailed schedule of tests.*
- ¹⁰ *Patients on an average daily dose of simvastatin 40 mg will be scheduled for additional Visits T4.1 and T5.1 to monitor clinical laboratory assessments and AE and SAE occurrence. These patients will also be contacted by telephone at Visits T4.2 and T5.2 to monitor AE and SAE occurrence.*
- ¹¹ Basic fasting lipids include total cholesterol, calculated LDL-C, HDL-C, non-HDL-C, and triglycerides. Repeat within 1 week if exceed protocol-specified criteria.
- ¹² Diet and exercise counseling per local and/or regional guidelines for the management of hyperlipidemia.
- ¹³ *Patients randomized after Protocol Amendment 3 and subsequent amendments are excluded from PK sampling.*
- ¹⁴ IWRS contact at either an early withdrawal or an EOS visit to register study discontinuation visit date.
- ¹⁵ Depending upon the length of time between visits, 1 or 2 bottles of study medication will be dispensed as instructed by IWRS. The bottle dispensed at Visit T1 will be returned to clinic at Visits T2 and T3 for evaluation of compliance and returned for continued use.
- ¹⁶ *If patient is discontinuing treatment and completing the EOS visit, but will be continuing in the study either by returning to clinic or by phone, continue to schedule study visits for the patient according to the protocol Schedule of Events*

Appendix 2: Adverse Event of Special Interest (AESI)

Adverse Event Terms per Protocol	Associated MedDRA Preferred Terms
Creatine kinase elevations	Blood creatine phosphokinase abnormal
Creatine kinase elevations	Blood creatine phosphokinase increased
Creatine kinase elevations	Blood creatine phosphokinase MM abnormal
Creatine kinase elevations	Blood creatine phosphokinase MM increased
New onset or worsening diabetes mellitus	Blood glucose abnormal
New onset or worsening diabetes mellitus	Blood glucose increased
New onset or worsening diabetes mellitus	Diabetes mellitus
New onset or worsening diabetes mellitus	Diabetes mellitus inadequate control
New onset or worsening diabetes mellitus	Diabetic ketoacidosis
New onset or worsening diabetes mellitus	Glucose tolerance impaired
New onset or worsening diabetes mellitus	Glucose urine present
New onset or worsening diabetes mellitus	Glycosuria
New onset or worsening diabetes mellitus	Glycosylated haemoglobin increased
New onset or worsening diabetes mellitus	Hyperglycaemia
New onset or worsening diabetes mellitus	Impaired fasting glucose
New onset or worsening diabetes mellitus	Ketoacidosis
New onset or worsening diabetes mellitus	Ketosuria
New onset or worsening diabetes mellitus	Ketosis
New onset or worsening diabetes mellitus	Type 2 diabetes mellitus
New onset or worsening diabetes mellitus	Urine ketone body present
Hepatic disorders	Alanine aminotransferase abnormal
Hepatic disorders	Alanine aminotransferase increased
Hepatic disorders	Aspartate aminotransferase abnormal
Hepatic disorders	Aspartate aminotransferase increased
Hepatic disorders	Blood bilirubin abnormal
Hepatic disorders	Blood bilirubin increased
Hepatic disorders	Hepatic enzyme abnormal
Hepatic disorders	Hepatic enzyme increased
Hepatic disorders	Hypertransaminaseaemia
Hepatic disorders	Liver function test abnormal
Hepatic disorders	Liver function test increased
Hepatic disorders	Transaminases abnormal
Hepatic disorders	Transaminases increased
Hypoglycemia	Blood glucose abnormal
Hypoglycemia	Blood glucose decreased
Hypoglycemia	Hypoglycaemia
Hypoglycemia	Hypoglycaemic coma
Hypoglycemia	Hypoglycaemic encephalopathy
Hypoglycemia	Hypoglycaemic seizure
Hypoglycemia	Shock hypoglycaemic
Metabolic acidosis	Metabolic acidosis
Muscular disorders	Muscular weakness
Muscular disorders	Muscle necrosis

Muscular disorders	Muscle spasms
Muscular disorders	Myalgia
Muscular disorders	Myoglobin blood increased
Muscular disorders	Myoglobin blood present
Muscular disorders	Myoglobin urine present
Muscular disorders	Myoglobinaemia
Muscular disorders	Myoglobinuria
Muscular disorders	Myopathy
Muscular disorders	Myopathy toxic
Muscular disorders	Necrotizing myositis
Muscular disorders	Pain in extremity
Muscular disorders	Rhabdomyolysis
Neurocognitive/Neurologic disorders	Amnesia
Neurocognitive/Neurologic disorders	Cognitive disorder
Neurocognitive/Neurologic disorders	Confusional state
Neurocognitive/Neurologic disorders	Disorientation
Neurocognitive/Neurologic disorders	Memory impairment
Neurocognitive/Neurologic disorders	Mental status changes
Renal disorders	Acute kidney injury
Renal disorders	Acute prerenal failure
Renal disorders	Blood creatinine abnormal
Renal disorders	Blood creatinine increased
Renal disorders	Blood urea abnormal
Renal disorders	Blood urea increased
Renal disorders	Blood urea nitrogen/Creatinine ratio increased
Renal disorders	Creatinine renal clearance abnormal
Renal disorders	Creatinine renal clearance decreased
Renal disorders	Glomerular filtration rate abnormal
Renal disorders	Glomerular filtration rate decreased
Renal disorders	Gout
Renal disorders	Oliguria
Renal disorders	Prerenal failure
Renal disorders	Renal failure
Renal disorders	Renal function test abnormal
Renal disorders	Renal impairment

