#### Monitoring and Management of Potential AEs and Adverse Events of Special Interest (AESI)

##### Adverse Events Associated with Experience with ETC-1002 to Date:

Small group mean increases in uric acid and homocysteine, and decreases in hemoglobin have been observed, but in general, these shifts have not been associated with clinical symptoms. Clinical labs and hematology will be monitored throughout the study.

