5.4.2 Adverse Events of Special Interest

Adverse events of special interest (AESI) will be identified based a pre-defined list of prefer terms provided by the sponsor (Appendix 2).

AESI will be presented in a listing and summarized by SOC, PT and treatment group.

In addition to adverse events, AESI is also being evaluated based on safety lab parameters. The details are provided in 5.4.6.

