5.4.6 Laboratory Evaluations

Continuous laboratory parameters (serum chemistry, hematology, coagulation (only at screening after amendment 3 and for those patients receiving anti-coagulation), urinalysis, urinalysis [microscopic]) listed in Table 4; fasting serum glucose, and HbA1c will be summarized using descriptive statistics for the observed value and the change from baseline by history of diabetics. Missing values for any of the laboratory evaluations will not be imputed; that is, only observed case data will be used. Baseline is defined as the last value prior to the first dose of study medication. Categorical urinalysis data will be listed, but will not be summarized.

As part of the AESI evaluation, below safety lab abnormality will be summarized by treatment group. All post-baseline lab values are being considered. Further details are provided in Section 5.4.6.1 through 5.4.6.4.

- ALT or AST (> 3x ULN and >5xULN)
- TB (> 2x ULN)
- Potential Hy's Law case: (ALT and/or AST > 3xULN with concurrent TB > 2xULN)
- CK (> 5x ULN) and (>10x ULN)
- Fasting Serum Glucose (mg/dL) (≤ 50 , and ≥ 126) by history of diabetics
- HbA1C ($\geq 6.5\%$) by history of diabetics
- Creatinine (change from baseline for >1 mg/dL)
- eGFR (< 15 mL/min/1.73m², 15 < 30 mL/min/1.73m²)
- Hgb (g/dL) (decrease from baseline for ≥ 2 g/dL)
- Hgb (<8 g/dL)

Table 4: Clinical Laboratory Parameters (Safety)

Hematology 
 • Hematocrit (Hct) • Hemoglobin (Hgb) • Mean corpuscular hemoglobin (MCH) • Mean corpuscular hemoglobin concentration (MCHC) • Mean corpuscular volume (MCV) • Platelet count • Red blood (RBC) cell count • White blood (WBC) cell count with differential (absolute and %) 	Blood Chemistry (serum, fasting) 
 • Albumin (Alb) • Alkaline phosphatase (Alk-P) • Alanine aminotransferase (ALT; SGPT) • Aspartate aminotransferase (AST; SGOT) • Blood urea nitrogen (BUN) • Calcium (Ca) • Carbon dioxide (CO₂) • Chloride (Cl) • Creatinine • Creatine kinase (CK) • Glucose • Lactate dehydrogenase (LDH) • Phosphorus • Potassium (K) • Sodium (Na) • Total and direct bilirubin (TB) • Total protein • Uric acid

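### The preferred-term definition of AESI in SAP Appendix 2 is incomplete: every hepatic term is a laboratory finding, and haemoglobin decrease has no event term

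*SAP*

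**What the plan says.** SAP section 5.4.2 states that AESI "will be identified based a pre-defined list of prefer terms provided by the sponsor", and refers to Appendix 2 for the list. It then says "AESI will be presented in a listing and summarized by SOC, PT and treatment group". Section 5.4.1 gives AESI a line in the TEAE overview, a patient incidence, and summaries by SOC, preferred term and maximum severity within the subgroups of section 5.2.5.

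There is also a laboratory component. Section 5.4.2 adds: "In addition to adverse events, AESI is also being evaluated based on safety lab parameters". Section 5.4.6 introduces its cut-offs with "As part of the AESI evaluation, below safety lab abnormality will be summarized by treatment group". They cover ALT, AST, total bilirubin, potential Hy's law cases, CK, fasting glucose, HbA1C, creatinine, eGFR and haemoglobin.

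Appendix 2 lists preferred terms under eight categories. The hepatic category consists of enzyme, bilirubin and liver-test terms such as "Liver function test abnormal". The term "Blood glucose abnormal" is entered twice, once under diabetes and once under hypoglycaemia.

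The protocol synopsis, on experience with the drug to date, reports that "decreases in hemoglobin have been observed". It describes the group mean shifts as small and in general without clinical symptoms. Uric acid increases are named in the same sentence.

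Protocol section 11.2.3 asks investigators to record a specific disease or syndrome where possible instead of its individual signs, and to report a cluster of findings with one cause as a single event.

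**The concern.** General safety is the primary endpoint of this trial, and the AESI line is where a reader looks first for organ-specific harm. If the list admits only laboratory-coded liver events, the AESI figures leave out the events that investigators were most certain about: the recording rule in protocol section 11.2.3 steers a diagnosed liver injury to a diagnosis term that is not on the list. A subgroup comparison of AESI would have the same gap.

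Haemoglobin raises a question of consistency. The SAP treats a haemoglobin fall as part of the AESI evaluation on the laboratory side, but an anaemia event reported by an investigator does not count as an AESI on the event side.

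**Working it through.** The documents state no figure on this point, so there is none to reproduce. The check is a count of Appendix 2, set beside the laboratory cut-offs in SAP section 5.4.6.

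| Appendix 2 category | Rows | Contains a clinical event or diagnosis? | Laboratory counterpart in section 5.4.6 |
|---|---|---|---|
| Creatine kinase elevations | 4 | No (a laboratory category by name) | CK >5x and >10x ULN |
| New onset or worsening diabetes | 16 | Yes, e.g. Type 2 diabetes mellitus | Glucose ≥126 mg/dL, HbA1C ≥6.5% |
| Hepatic disorders | 13 | No | ALT/AST >3x and >5x ULN, TB >2x ULN, potential Hy's law |
| Hypoglycemia | 7 | Yes, e.g. Hypoglycaemic coma | Glucose ≤50 mg/dL |
| Metabolic acidosis | 1 | Yes | None |
| Muscular disorders | 14 | Yes, e.g. Rhabdomyolysis | CK, as above |
| Neurocognitive/neurologic | 6 | Yes, e.g. Amnesia | None |
| Renal disorders | 17 | Yes, e.g. Renal failure | Creatinine, eGFR |
| (no category) | 0 | – | Hgb decrease ≥2 g/dL, Hgb <8 g/dL |

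Rows: 4 + 16 + 13 + 7 + 1 + 14 + 6 + 17 = 78. One term appears twice, so there are 78 − 1 = 77 distinct terms.

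**Hepatic.** 0 of 13 terms is a clinical liver event. Take a patient whose hepatitis is recorded as a single event under the rule in protocol section 11.2.3:

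1. The preferred term is not in Appendix 2, so section 5.4.2 does not classify the event as an AESI.
2. The event is therefore absent from the AESI overview line, AESI patient incidence, AESI by SOC and preferred term, and AESI by subgroup.
3. It is present in TEAEs by SOC, preferred term and severity and, if applicable, in the SAE, fatal and withdrawal outputs of section 5.4.1.
4. It is present in the laboratory AESI summary only if a study sample crosses a cut-off. Section 5.4.6 uses all post-baseline values, but the SAP does not say that a laboratory hit enters the AESI overview or patient incidence.

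If the investigator also records a separate listed event, such as an increased ALT, the patient is counted through that event. The gap concerns patients whose liver event is recorded only as a diagnosis.

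**Haemoglobin.** 0 of 77 terms denotes anaemia or decreased haemoglobin. The one term that contains the word is the glycosylated haemoglobin term, under diabetes. Every other analyte in the section 5.4.6 list has event terms in Appendix 2.

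**Glucose.** Assigning the duplicated term to one category takes the list from 78 to 77 rows and leaves 77 distinct terms. Since the AESI tables are by SOC and preferred term, no planned count changes.

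**Direction of the correction.** Adding terms can raise AESI incidence or leave it unchanged. It cannot lower it.

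**The case against.** The strongest reply is that nothing is lost from the report. Clinical liver events and anaemia appear in the full TEAE and SAE tables and in the listings. Liver injury that moves enzymes or bilirubin past the cut-offs is caught by the laboratory component whatever the investigator wrote, and potential Hy's law cases are listed. Haemoglobin is also inside the AESI evaluation through its laboratory criteria. The SAP summary of changes says the term list was updated on recent data and DMC advice. This stands as a limit on the harm. It does not explain why the liver list alone omits diagnoses when the renal and muscular lists include them, and it does not put those events into the AESI figures.

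A reader might go further and infer any of the following. The documents do not support them.

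- *AESI incidence will be wrong.* Incidence under the stated definition is well defined. The definition is incomplete.
- *One glucose event will show as both high and low.* No table by Appendix 2 category is specified, and the overview counts a patient at most once in each AE category. The ambiguity matters only if category counts are added.
- *Haemoglobin was left out of AESI.* It has a laboratory criterion and lacks only an event term. Protocol section 11.4 and the AESI part of section 12.5 are largely blacked out, so it cannot be said whether the protocol named anaemia as an AESI.
- *Uric acid was ignored.* Gout is a listed term, and uric acid is in the chemistry panel, summarised by value, change and out-of-range counts.
- *About 6 or 7 active and 3 placebo patients would be missed.* That is 0.005 × 1300 = 6.5 and 0.005 × 650 = 3.25. The 0.5% is the lowest placebo event rate quoted from a study of another drug for the sample-size section, and is not a rate for these terms.

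**Conclusion.** The event-term definition of AESI is incomplete in two respects. The hepatic category has no clinical term (0 of 13), so liver events recorded only as diagnoses drop out of every AESI event table. Haemoglobin decrease has a laboratory criterion but no event term (0 of 77), which is inconsistent with how the SAP treats CK, liver, glucose and renal function.

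The number of patients affected cannot be computed from the documents. The general safety tables and the laboratory component limit the consequence to the AESI outputs themselves. The conclusion assumes that investigators follow the recording rule in protocol section 11.2.3, and that laboratory hits do not feed the AESI overview and incidence, since the SAP does not say that they do. It is a gap worth closing because the remedy needs no new data.

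**What to change.** Add to Appendix 2:

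- clinical hepatic preferred terms (hepatitis, jaundice, drug-induced liver injury, hepatic failure and related terms), or a standard MedDRA query for drug-related hepatic disorders;
- anaemia and haemoglobin-decreased terms;
- optionally, blood uric acid increased and hyperuricaemia.

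Keep the glucose term that is entered twice as an AESI term, because deleting it from both categories would lose events. State whether incidence by Appendix 2 category will be reported. If it will, assign each such event to one category by the direction of the patient's glucose value.

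Rerun the AESI overview line, patient incidence, SOC and preferred-term table and subgroup tables on the extended list, and keep the current list as a second tabulation so that the effect of the change is visible. The cost is programming for several tables, and AESI counts may rise slightly.
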